#### **5.4.3 Time-to-event Analysis for the Secondary Effectiveness Endpoints**

Time-to-event analysis may be applied to the events of interest, along with Kaplan-Meier plot by treatment when deemed appropriate.

## 5.5 Exploratory Endpoints

All analyses will be performed on the mITT, PP, i-CABG mITT, and i-CABG PP populations.

The descriptive statistics will be summarized by treatment group for the exploratory endpoints.

Percent difference in pre-CPB vs. post-CPB blood TAM levels as measured by LC/MS-MS will be analyzed in the same fashion as blood ticagrelor levels (Section 5.3). Two-sample t-test for the percentage change in blood TAM between the treatment and the control group will be performed and the p-value and 95% CI for this treatment difference will be provided. Wilcoxon rank sum test based on the observed data will be performed as a sensitivity analysis. The nonparametric p-value will be provided as well as median treatment difference in percent change between pre-CPB and post-CPB blood TAM levels.

If the post-CPB blood TAM level is below the limit of quantification (BLQ), the BLQ value will be assigned. The Last Measurable Observation Carried Forward method will be implemented to test the validity of imputation.

ANOVA model will be employed to compare area under the concentration time curve (AUC) between the treatment groups, for intraoperative ticagrelor pharmacokinetic (PK) concentration and TAM based on the observed data.

The boxplots will be presented for the following exploratory endpoints by treatment.

- Operative time (measured from start of skin incision to completion chest closure)
- Duration of ICU stay
- Duration of hospital stay

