## 2 SAMPLE SIZE AND STATISTICAL POWER CONSIDERATION

The hypothesis for the primary effectiveness endpoint will be tested using Finkelstein-Schoenfeld test (Finkelstein et al 1999). With the assumed effect sizes and variability for Scenario 1 outlined in Table 1 (Section 11.1 of the CIP), 57 subjects per arm will provide >99% power for the primary effectiveness endpoint based on Finkelstein-Schoenfeld test statistics at the two-sided significant level alpha ( $\alpha$ ) of 0.05. Taking into consideration higher than anticipated variability observed with the 24hr CTD variable, in scenario 2 we consider the same effect sizes in the 3 components and a larger variability (double of that in Scenario 1). In that instance the needed sample size is 65 per arm to achieve 92% power.

With this same sample size per arm, power for the key secondary endpoint is estimated >99.9%, and for 24-hour chest tube drainage (mL), >99.9%, based on a two-sample t-test assuming equal variance and a two-sided alpha of 0.05. Assuming unequal variances, power for comparisons of platelet transfusions (volume [mL]) and PRBC transfusions (volume [mL]), is estimated at 98.0% and 96.7%, respectively.

Allowing for ~7% dropouts, approximately 140 subjects will be randomized in a 1:1 ratio to the treatment and control arms to ensure that 130 subjects (65 per arm) will be evaluable for the primary effectiveness analysis.

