#### 3.3 Randomization/Blinding

All subjects will be randomized in a one to one (1:1) ratio to either the control arm (SoC) or the treatment arm (SoC + DrugSorb™-ATR device). Pre-randomization stratification will be performed by study site, and by type of intended surgical procedure - either:

- CABG alone (irrespective of number of grafts); or
- All other cardiothoracic procedures (including but not limited to combination procedures [i.e., CABG + aortic/mitral valve procedures, double heart valve procedures, etc.], aortic interventions, and combination aortic + cardiac interventions).

Of note, patients undergoing undergo CABG + minor add-on procedures (e.g., left atrial appendage clipping, IABP or Impella placement, etc.) that do not (in the opinion of the investigator) significantly increase operative complexity or bleeding risk are included in the CABG alone category for Type of planned cardiothoracic surgery. Please see Section 6.1 of the CIP for additional details of pre-randomization stratification. Randomization is implemented via an Interactive Voice/Web response (IxRS) system.

Neither the subjects nor the site personnel have the treatment assignment information during the study period, unless specified in **Section 6.3** of the CIP. The blinded study team is blocked from every subject's treatment assignment before the data base lock for unblinding. Please see **Section 6.3** of the CIP for additional details of study blinding.

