### **5 STATISTICAL ANALYSIS METHODS**

#### **5.1 General Considerations**

Unless otherwise specified, all statistical analyses will be performed on the mITT population.

In general, summary statistics (n, mean, SD, median, minimum, and maximum for continuous variables, and number and percentage of subjects in each category for categorical variables) will be provided by treatment. All summary tables will be based on the observed data unless specified otherwise. Source data for the summary tables and statistical analyses will be presented as subject level data listings.

The two-sided significance level of 5% is used for the hypothesis testing, unless specified otherwise.

Fixed sequence testing procedure will be utilized to compare the effectiveness of the treatment vs control in the following order:

Primary endpoint → Key secondary endpoint → Additional Secondary endpoints (24hr CTD → platelet transfusions → PRBC transfusions → UBPB events by class → surgical re-exploration for excessive bleeding → fatal perioperative bleeding event)

The significance for the secondary endpoints will only be considered if the primary endpoint is declared statistically significant and the p-value of the previous endpoint is less than 5%, otherwise, the testing procedure stops, and all the subsequent p-values will be nominal.

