#### A 1.1.4 Pharmacokinetic Parameters

The following plasma PK parameters of ticagrelor and TAM will be determined with actual sampling time points using noncompartmental methods as appropriate:

Parameters	Description
AUC 0-t	Area under the plasma concentration vs time curve (AUC) from pre-dose (time 0) to the last quantifiable plasma concentration (C last )

No PK parameters will be calculated for subjects with 2 or fewer detectable concentrations in their PK profile.

AUC and plasma concentration for ticagrelor and TAM at each sampling timepoint (Pre-CPB, 30min, 60min, 90min, 120min, and post-CPB) will be compared between control and DrugSorb using a two-sample t-test, and if parametric assumptions are not met, then via a Mann-Whitney test.

The sample SAS code for this analysis is included here

```
proc ttest data=ADPP sides=2 alpha=0.05 h0=0;
  class TREATMENT;
  var log_PKParm;
  ods output ConfLimits=CL Statistics=Stat Ttests=Ttest;
```

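### SAP 5.5 and Appendix A 1.1.4 do not give one AUC analysis: scale, model terms and the switch to Mann-Whitney are left open

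*SAP*

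**What the plan says.** SAP 5.5 (Exploratory Endpoints) says: "ANOVA model will be employed to compare area under the concentration time curve (AUC) between the treatment groups", and continues "for intraoperative ticagrelor pharmacokinetic (PK) concentration and TAM based on the observed data". No transformation, factor or covariate is named, and no effect measure is given.

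SAP Appendix A 1.1.4 covers the same AUC, for the same two analytes and the same two arms. AUC and the concentration at each sampling time "will be compared between control and DrugSorb using a two-sample t-test, and if parametric assumptions are not met, then via a Mann-Whitney test". The assumption check and the threshold that would trigger the second test are not given. The sample code below that sentence begins "proc ttest data=ADPP sides=2 alpha=0.05 h0=0" and analyses "var log_PKParm", a log-scale variable. Neither the sentence above the code nor SAP 5.5 mentions a log.

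SAP Section 9 sends the reader to Appendix A for the pharmacokinetic plan but does not say that it replaces 5.5. Protocol 11.3 leaves the methods for exploratory endpoints to the SAP, so it does not settle the matter.

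**The concern.** Two programmers could each follow the SAP faithfully and report different things: a difference in mean AUC, a ratio of geometric means, or a rank comparison. SAP A 2.0 requires independent double programming, so the ambiguity would probably surface only at that stage, after unblinding, and would then be settled with the data in view. An untriggered switch to Mann-Whitney has the same weakness, because the choice of test is left to a judgement made on the data being tested.

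At stake are the estimate, its interpretation and, in some settings, the side of 0.05 on which the p-value falls. No confirmatory claim depends on AUC.

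**Working it through.** **1. The texts side by side.**

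| | SAP 5.5 | A 1.1.4 sentence | A 1.1.4 sample code |
|---|---|---|---|
| Test | ANOVA | two-sample t, or Mann-Whitney | t-test |
| Scale | not stated | not stated | log |
| Other factors | none named | none | none |
| Rule for switching | none | assumptions not met; no check given | none |

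**2. ANOVA against the t-test.** With two groups and treatment as the only term, F = t². In one simulated data set with 65 per arm:
- raw scale: t² = F = 2.4935, p = 0.1168 by both;
- log scale: t² = F = 4.1361, p = 0.0440 by both.

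The name of the test changes nothing. In this example the scale alone moved p across 0.05.

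**3. Inputs for the size of the effect.** From the documents: two arms, 1:1 (SAP 3.3, "All subjects will be randomized in a one to one (1:1) ratio to either the control arm (SoC) or the treatment arm"); 65 per arm (SAP Section 2, "ensure that 130 subjects (65 per arm) will be evaluable for the primary effectiveness analysis"); two-sided 0.05 (A 1.1.4 code). The documents give no effect, SD or power for AUC, so there is no stated AUC figure to reproduce. As a check of the power routine only, the key secondary endpoint (57 per arm, difference 40, SD 40) has noncentrality 40 / (40·√(2/57)) = 5.34 and power 0.9996, in line with the stated >99.9%.

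Assumed, not in the documents: lognormal AUC, CV 50%, 100% or 150%, and device/control geometric mean ratio 1.0 to 0.6. The log-scale SD is σ = √ln(1 + CV²), which gives 0.472, 0.833 and 1.086.

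**4. Simulation, 10,000 runs per setting, 65 per arm (selected rows).** The first three result columns are rejection rates at 0.05.

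| CV | Ratio | Raw t/ANOVA | Log t | Mann-Whitney | Raw and log verdicts differ | Log and rank verdicts differ |
|---|---|---|---|---|---|---|
| 50% | 0.8 | 0.718 | 0.763 | 0.742 | 8.6% | 5.5% |
| 50% | 0.6 | 1.000 | 1.000 | 1.000 | 0.0% | 0.0% |
| 100% | 0.7 | 0.538 | 0.672 | 0.646 | 19.3% | 7.2% |
| 150% | 0.6 | 0.531 | 0.762 | 0.742 | 27.5% | 5.5% |

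With 57 per arm the raw-log disagreement ranged from 0.1% to 26.7%. Pooled and Satterthwaite versions of the raw t-test differed in at most 0.3% of runs, so that choice does not matter here.

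**5. No true effect (ratio 1.0).** At 65 per arm each single test rejected in 4.5% to 5.1% of runs. Taking whichever of the three was significant rejected in 6.8%, 7.6% and 8.2% of runs at CV 50%, 100% and 150%. At 57 per arm the figures were 7.3%, 7.8% and 7.9%.

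**6. What the pre-CPB covariate adds.** Adjusting log AUC for log pre-CPB concentration multiplies the residual SD by √(1 − ρ²), where ρ is their correlation. Assume ratio 0.80, CV 80% and 55 per arm (an assumed number with usable profiles, below the planned 57 or 65).
- σ = √ln(1.64) = 0.703.
- Standard error without the covariate = 0.703·√(2/55) = 0.134.
- Noncentrality = |ln 0.80| / 0.134 = 0.223 / 0.134 = 1.66.

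| Analysis | Noncentrality | Power |
|---|---|---|
| Log t-test | 1.66 | 0.38 |
| ANCOVA, ρ = 0.3 | 1.66/0.954 = 1.74 | 0.41 |
| ANCOVA, ρ = 0.5 | 1.66/0.866 = 1.92 | 0.48 |
| ANCOVA, ρ = 0.8 | 1.66/0.600 = 2.77 | 0.78 |

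The powers are simulated, and the formula agrees to within 0.01. The documents do not give ρ. Some correlation is plausible, because AUC0-t in A 1.1.4 starts at the pre-dose sample, so that concentration enters the area directly.

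**The case against.** The strongest case against the point is that little separates the two sections. The ANOVA of 5.5, run on log AUC with treatment only, would be exactly the test in the sample code. Section 9 marks Appendix A as the detailed plan, and Mann-Whitney is a conditional fallback in the same sentence as the t-test. On that view one editorial line naming the scale and the fallback rule is enough, and ANCOVA is a preference. Much of this stands. It leaves the scale unstated in both texts, the trigger undefined, and no rule on which section governs.

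Four stronger readings are tempting, and the documents do not support them:
- **Three rival tests.** The ANOVA and the t-test coincide on a given scale, and the rank test is a fallback.
- **5.5 prescribes the raw scale because it refers to observed data.** Elsewhere the SAP uses that phrase for data that are not imputed. In 5.1, for example: "All summary tables will be based on the observed data unless specified otherwise". It says nothing about transformation.
- **AUC is the only exposure summary.** A 1.1.4 also compares concentrations at each sampling time, and the key secondary endpoint is the percent change from pre- to post-CPB.
- **Protocol 11.3 says patients' baseline levels are highly variable.** That remark is about benchtop studies. It cannot be used as evidence for a high ρ or a high CV in this trial.

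**Conclusion.** The inconsistency is real and its consequence is small. SAP 5.5 and A 1.1.4 leave open the scale, the model terms, the effect measure and the rule for switching tests. Raw versus log is the choice that matters most: the two verdicts differ in about 0% to 28% of trials across the assumed CVs and ratios, and hardly at all when the effect is large and the CV small. The 7-8% false-positive rate is for picking the most favourable of three tests. The SAP does not plan that; the figure shows what the unspecified choice would permit.

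All these figures rest on an assumed lognormal AUC with assumed CVs and ratios. The gain from the covariate also rests on an assumed correlation and runs from slight (0.41 against 0.38) to large (0.78 against 0.38). AUC is exploratory and lies outside the fixed testing sequence in SAP 3.7, so this is a low-cost improvement and does not threaten the trial's conclusions.

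**What to change.** State one analysis in identical words in SAP 5.5 and A 1.1.4: ANCOVA of log AUC on treatment and log pre-CPB concentration, reported as a device/control geometric mean ratio with 95% CI. Remove the separate ANOVA sentence from 5.5 and the switch to Mann-Whitney for AUC from A 1.1.4. Keep a rank test as a labelled sensitivity analysis, reported whatever the main result. Replace the sample code with code for this model. Add a line on how a missing or below-quantification pre-CPB value is handled, because the log needs a positive number.

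The cost is a few lines of SAP text and one code block. The pre-CPB sample is already scheduled and is taken before bypass starts, so no new data are needed. If the covariate is not wanted, the minimum repair is to name the scale, the model terms and the effect measure once, and to delete the switch or give it an explicit rule.

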## 6 SAFETY ANALYSES

### 6.1 General Considerations

All safety endpoints will be analyzed by treatment on the SA and i-CABG SA populations unless specified otherwise. All safety data will be listed on the SA Population.

### 6.2 Adverse Events

An adverse event (AE) is any untoward medical occurrence (signs, symptoms, abnormal laboratory findings) in a subject regardless of relationship to the device or procedure. All AEs that occur starting from subject enrollment through follow-up will be reported. Adverse events (AEs) will be coded using the most recent version of Medical Dictionary for Regulatory Activities (MedDRA). The version of MedDRA® will be provided in a footnote on outputs.

Treatment-emergent AEs (TEAEs) are defined as AEs with onset or worsening in severity after the start of the cardiopulmonary bypass procedure, and within 30 days after study treatment. Analyses of AEs will include only TEAEs. The incidence of treatment-emergent AEs (TEAE) will be summarized by treatment group, and overall. Non-TEAEs (i.e., AEs that

occur following informed consent but prior to the start of CPB) will not be summarized but will instead be provided in a separate listing.

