11.6. Safety Analysis

All the safety endpoints will be analyzed in the SA Population. Additional safety analyses will be conducted on the mITT and PP Population if they are different from the SA population.

The incidence of all AEs occurring after the start of the CPB procedure will be summarized by treatment group using frequency and percentage. AEs that occur following informed consent but prior to the start of CPB will not be included in this safety analysis but will be provided in a listing. Within the Safety Analysis, AEs will be summarized by severity and relationship to the study device as determined by the Investigator (or designee). Discontinuations due to AEs, and SAEs will be summarized. All AEs will be coded using the Medical Dictionary for Regulatory Activities (MedDRA®) according to system organ class and preferred term, prior to database lock.

Observed values for clinical laboratory test data and vital signs, along with change from baseline results, will be summarized by collection time point. A summary of clinically notable values will be provided.

All the safety data will be listed in the SA population. Further details regarding presentation and analysis of safety data will be detailed in the SAP.

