20. APPENDICES

Appendix 1: Adverse Event Reporting

An adverse event (AE) is any untoward medical occurrence (signs, symptoms, abnormal laboratory findings) in a subject regardless of relationship to the device or procedure. Throughout the study, the Investigator or designee will determine adverse event (AE) occurrences. All AEs that occur starting from subject enrollment through follow-up will be reported. As a matter of semantics, AEs that are new onset or worsen in severity *after the start of the cardiopulmonary bypass procedure* are considered Treatment-emergent AEs. This term does *not* include adverse events occurring *prior* to the start of CPB but *after* the signing of the ICF (assent or consent). As previously discussed in **Section 11.6**, only the treatment-emergent AEs will be included in the safety analysis. This will be further detailed in the SAP.

Each adverse event is considered to be either anticipated or unanticipated as described below. The site is required to report the classes of adverse events that occur in the study (AE, SAE, and UADE) as described further below.

Severity Assessment

The Investigator will assess each adverse event for severity in accordance with the following categories: mild, moderate, severe, life-threatening, or death.

The severity assessment is distinct from the seriousness assessment (see definition of SAE below).

Serious Adverse Events

A serious AE (SAE) is defined as any untoward medical occurrence that meets one or more of the following criteria:

- led to death;
- led to a life-threatening illness or injury;
- led to in-patient hospitalization or prolongation of existing hospitalization;
- led to disability or permanent damage to a body structure or body function;
- led to fetal distress, fetal death, congenital anomaly or birth defect;
- required medical or surgical intervention to prevent permanent impairment or damage; or
- Important medical events that may not result in death, be life-threatening, or require hospitalization may be considered SAEs when, based upon appropriate medical judgment, they may jeopardize the subject and may require medical or surgical intervention to prevent one of the outcomes listed in this definition.

Definition of Hospitalization

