Adverse events requiring hospitalization or extended hospitalization should be considered serious. In general, hospitalization signifies that the subject has been detained (usually involving an overnight stay) at the hospital or emergency ward for observation and/or treatment. When in doubt as to whether hospitalization occurred or was necessary, the AE should be considered as serious. *Planned hospitalization for pre-existing condition, or a procedure required by the Clinical Investigation Plan, without a serious deterioration in health is not considered a serious adverse event.*

Serious AEs occurring after 30 days post-operation are to be reported to the Sponsor if, in the judgment of the Investigator, there is an association between the event and the previous use of the device under investigation.

Causality Assessment

The Investigator will assess each adverse event for relationship to the following (causality), and relationship classified as unrelated, unlikely related, possibly related, probably related, or definitely related:

Investigational Treatment/Device: An investigational device/treatment-related adverse event is one which in the judgment of the Investigator, results as a consequence of the investigational device/treatment. Clinical judgement in conjunction with the relevant documents, such as the Investigator's Brochure and the Clinical Investigational Plan shall be applied in the determination of whether the AE might be related to the device/treatment. The presence of confounding factors, such as concomitant medication/treatment, the natural history of the underlying disease, other concurrent illness or risk factors shall be considered.

Surgical Procedure: The investigator will distinguish between the events potentially related to CPB and the investigational device from those related to the underlying surgical procedures. A procedure-related adverse event is one which, in the judgment of the Investigator, results as a consequence of the subject's surgical procedure and is not specific to the investigational device/treatment used or the associated CPB circuit. Complications occurring during a procedure are considered not related to the device if the complication would have been applied to the subjects in the absence of the investigational device use/application. Adverse events that have previously been determined to be related to the investigational device should not also be assessed as being related to the surgical procedure.

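### The SAP's 30-day limit on treatment-emergent AEs, absent from the protocol's definition, can keep late device-related serious events out of the safety summary tables, though not out of the listings

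*SAP*

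**What the plan says.** **SAP.** Section 6.2 gives treatment-emergent AEs (TEAEs) an upper bound and makes them the only AEs analysed: "and within 30 days after study treatment. Analyses of AEs will include only TEAEs". It describes non-TEAEs solely as events between consent and bypass, which "occur following informed consent but prior to the start of CPB) will not be summarized but will instead be provided in a separate listing". Section 6.3, on the analysis of TEAEs, holds the overview table and all tables by system organ class and preferred term. Among them are the tables for device-related serious AEs (SADEs) and for unanticipated device effects (UADEs). Sections 6.2.3 and 6.2.4 say that ADEs and UADEs will be summarised by arm and overall, and set no day limit. Section 6.3 also provides listings of AEs and SAEs, and section 6.1 lists all safety data for the safety population.

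**Protocol.** Section 11.6 states: "The incidence of all AEs occurring after the start of the CPB procedure will be summarized by treatment group using frequency and percentage". Appendix 1 defines treatment emergence by onset or worsening after bypass begins, gives no end date, and says "only the treatment-emergent AEs will be included in the safety analysis". It adds a late duty: "Serious AEs occurring after 30 days post-operation are to be reported to the Sponsor if, in the judgment of the Investigator", there is an association with the device. Note n to Table 6 repeats that duty. Table 6 allows the final contact from POD 30 to POD 35.

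**Endpoint.** Both documents list serious device-related adverse events as an additional safety endpoint (protocol 4.3.6, SAP 1.3.6). Every other item in those lists is tied to 30 days or to the index hospitalisation. This one has no window.

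**The concern.** The SAP narrows the set of AEs that the protocol says will be summarised, and gives no reason. The narrowing falls on two kinds of event: AEs with onset in the last days before a late but in-window final contact, and serious events after day 30 that an investigator links to the device. The second kind bears directly on a named safety endpoint. SAP 6.4, which covers the additional safety endpoints, omits that endpoint, so it is reported only through the TEAE-based tables of 6.3. The 30-day limit thus becomes the endpoint's window by default. A SADE table could read zero while the SAE listing shows one. With 65 to 70 subjects per arm, readers will look at the table first.

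**Working it through.** The documents give no figure to reproduce. The check is to follow three illustrative events through the stated rules.

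| Event | Protocol 11.6 and Appendix 1 | TEAE under SAP 6.2 | Non-TEAE listing under SAP 6.2 | SAP 6.3 summary tables | AE/SAE listings |
|---|---|---|---|---|---|
| AE, onset POD 20 | summarised | yes | no | in | in |
| AE, onset POD 32, found at a contact on POD 34 | summarised | no | no | out | in |
| Device-related SAE, onset POD 40 | summarised, if it reaches the database | no | no | out | in, on the same condition |

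1. *Gap in classification.* The second and third events are too late to be TEAEs, and they are not pre-bypass events. The SAP puts them in neither class.
2. *Conflict inside the SAP.* If the third event is a device effect, 6.2.3 (or 6.2.4, if unanticipated) says it is summarised. The general sentence in 6.2 says it is not. A programmer cannot tell which governs.
3. *Final contact.* SAP 6.2 also says that AEs through follow-up will be reported, and the follow-up contact may take place up to POD 35. Section 6.4 allows 30 ± 5 days for adjudicated bleeding. That is a separate endpoint and need not share the TEAE window, but it shows that the SAP's authors knew of the later contact.

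**Scale, for illustration only.** Inputs: 65 evaluable subjects per arm (SAP section 2) and 70 randomised per arm (protocol synopsis). The late-event rate *p* is an assumption, because the documents give none.

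- Weight of one event: 1/65 = 1.54 percentage points; 1/70 = 1.43 percentage points.
- Chance of at least one late device-related SAE in the device arm: 1 − (1 − p)^n.

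| Assumed p | Expected events, n = 65 | Chance, n = 65 | Expected events, n = 70 | Chance, n = 70 |
|---|---|---|---|---|
| 0.1% | 0.07 | 6.3% | 0.07 | 6.8% |
| 0.5% | 0.33 | 27.8% | 0.35 | 29.6% |
| 1% | 0.65 | 48.0% | 0.70 | 50.5% |
| 2% | 1.3 | 73.1% | 1.4 | 75.7% |

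The range is wide because *p* is unknown. It does not show that an undercount is likely.

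**The case against.** The best defence is that the SAP only makes explicit a bound that the protocol already implies. The synopsis ends follow-up at 30 days, section 9.2.1 monitors subjects to the day-30 assessment, the primary safety endpoint covers the study period, and section 7.2 has the events committee adjudicate within 30 days. Appendix 1 and section 11.6 leave detail to the SAP. On this view the post-day-30 clause is a duty to inform the sponsor, outside the planned analysis. A 30-day TEAE window is a legitimate choice, and exposure is confined to bypass, so late device effects may be rare.

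Much of this stands. A reader might infer that the endpoint is in fact undercounted, or that the SAP discards the late events. The documents support neither. No passage says that the endpoint runs past day 30, an undercount needs an event to occur, and the listings retain the events. Nor do the documents say whether late reports enter the analysis database. Section 6.3.3 places lock after all 30-day assessments, so some reports could arrive too late. Late reports also depend on investigator judgement without a scheduled contact, so pooling them with the 30-day incidence would mix systematic with selective ascertainment.

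The defence does not explain the POD 31 to 35 gap, since the protocol's own final contact extends that far. It does not settle the conflict between 6.2 and 6.2.3–6.2.4. It also leaves the endpoint without a stated window. Protocol section 9.1 ends the investigation at the last subject's last contact, scheduled or not, so the study period is not plainly closed at day 30.

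**Conclusion.** The point holds as a mismatch between the SAP and the protocol, and within the SAP. Taken literally, SAP 6.2 excludes two kinds of event from the 6.3 tables: AEs with onset on POD 31 to 35 found at an in-window contact, and device-related SAEs reported after day 30. The SADE table, which carries the unwindowed endpoint, is among those affected. The effect is limited to summary tables and depends on such an event occurring. Each omitted event would be worth 1.4 to 1.5 percentage points in an arm of 70 or 65. The number of such events cannot be estimated from the documents. Effectiveness results are untouched.

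This conclusion rests on two readings: that the TEAE-only sentence in 6.2 governs the device-effect tables in 6.3, and that AE recording through follow-up extends to the actual date of the final contact. If 6.2.3 and 6.2.4 override 6.2, late ADEs and UADEs are already summarised, and the remaining fault is that the SAP does not say so.

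**What to change.** Make three changes before database lock.

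- **SAP 6.2:** extend the TEAE window from the start of bypass through the day-30 follow-up contact, which may fall up to POD 35, to agree with the protocol's definition and visit schedule.
- **SAP 1.3.6 and 6.4:** state the time window of the serious device-related AE endpoint and name the table that reports it.
- **SAP 6.3:** add a separate row by arm for device-related SAEs, SADEs and UADEs reported after that contact and before lock. Do not pool it with the fixed-window incidence. Refer to this row in 6.2.3 and 6.2.4, so that all these sections agree.

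The cost is a few sentences, one changed derivation flag and one table row. No new data collection is needed, provided that late reports sent to the sponsor are available to the analysis team at lock; the SAP should confirm this. The drawback is that late events are ascertained selectively, so the row is descriptive and cannot support a comparison of rates.
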